APPENDIX D- SURVEYS FOR AIM 1.2

References for survey questions from patient and provider are at the end of this appendix. Validated surveys were used whenever possible.

All surveys will be provided to patients on REDCap but can be done on paper when patient requests and then later submitted to REDCap by the study team.

****Baseline ('Pre') Patient Questionnaire****

Thank you for agreeing to participate in this study.

Study ID _____ (to be filled out by study team)

Date: _____

1. If your doctor or nurse asked you right now to make a choice about whether or not to get a mammogram, on a scale from 1-15 how certain are you about whether or not you would choose to get a mammogram in the next year? (1 means you are sure you would get a mammogram while 15 means you are sure you would not get a mammogram, if you are unsure please give a number between 1 to 15, 8 is the middle).

(If interview is being done over the phone because the in-person visit was missed, then ask patient: From 1-15, how likely are you to get a mammogram, 1 means you are certain I will get a mammogram and 15 means you are certain you will not get a mammogram. If you are not sure, please give a number between 1 and 15 that best describes how likely you are to get a mammogram)****

1	2	3	4	5	6	7	8	9	10	11	12	13	14	15
Will Get a Mammogram							Unsure				Will Not Get Mammogram			

As women age, the benefits of routine (when no symptoms are present) mammography may get smaller. As we try to learn from you, we would appreciate your honest answers to the questions below. These questions are about how you feel about whether or not to get a mammogram. Please say whether you Strongly Agree, Agree, are not sure, Disagree, or Strongly Disagree with the statements below.

2. I know which options are available to me for getting tested for breast cancer.

				
Strongly Agree	Agree	Not sure	Disagree	Strongly Disagree

3. I know the benefits of getting a mammogram.

				
Strongly Agree	Agree	Not sure	Disagree	Strongly Disagree

PROTOCOL TITLE:

4. I know the downsides or risks of getting a mammogram.

				
Strongly Agree	Agree	Not sure	Disagree	Strongly Disagree

5. I am clear about which benefits of getting a mammogram matter most to me.

				
Strongly Agree	Agree	Not sure	Disagree	Strongly Disagree

6. I am clear about which downsides or risks of getting a mammogram matter most to me.

				
Strongly Agree	Agree	Not sure	Disagree	Strongly Disagree

7. I am clear about whether the benefits of getting a mammogram are more important to me than the downsides or risks.

				
Strongly Agree	Agree	Not sure	Disagree	Strongly Disagree

8. I have enough support from others to make a choice whether or not to get a mammogram.

				
Strongly Agree	Agree	Not sure	Disagree	Strongly Disagree

9. I am choosing without pressure from others about whether or not to get a mammogram.

				
Strongly Agree	Agree	Not sure	Disagree	Strongly Disagree

10. I have enough advice to make a choice about whether or not to get a mammogram.

				
Strongly Agree	Agree	Not sure	Disagree	Strongly Disagree

11. I am clear about the best choice for me when it comes to getting a mammogram

				
Strongly Agree	Agree	Not sure	Disagree	Strongly Disagree

PROTOCOL TITLE:

12. I feel sure about what to choose in terms of whether or not to get a mammogram.

- Strongly Agree Agree Not sure Disagree Strongly Disagree

13. The decision whether or not to get a mammogram is easy for me to make.

- Strongly Agree Agree Not sure Disagree Strongly Disagree

14. I feel I have made an informed choice whether or not to get a mammogram.

- Strongly Agree Agree Not sure Disagree Strongly Disagree

15. My decision about whether or not to get a mammogram shows what is important to me

- Strongly Agree Agree Not sure Disagree Strongly Disagree

16. I expect to stick with my decision whether or not to get a mammogram

- Strongly Agree Agree Not sure Disagree Strongly Disagree

17. I am satisfied with my decision whether or not to get a mammogram.

- Strongly Agree Agree Not sure Disagree Strongly Disagree

The next set of questions are questions about mammograms in general. Your best guess is fine.

18. Among women aged 75 or older, who is more likely to die from breast cancer?

- Women who get mammograms
- Women who do NOT get mammograms
- There is almost no difference
- I don't know

19. The benefit of getting a mammogram is finding and treating a breast cancer when it is small and can be treated with only minor surgery.

- True False

20. Getting a mammogram will prevent me from getting breast cancer.

- True False

21. Most women who have an abnormal mammogram have breast cancer.

PROTOCOL TITLE:

- True False

22. Women aged 75 or older have a higher chance of getting breast cancer than younger women.

- True False

23. More women aged 75 or older die of heart disease than breast cancer.

- True False

24. Your other health problems should affect whether or not you get a mammogram.

- True False

25. Some breast cancers found by a mammogram would never have shown up or caused problems in a woman's lifetime. .

- True False

26. Most women aged 75 or older with breast cancer are treated with chemotherapy.

- True False

27. Some breast cancers are not detected by mammograms.

- True False

28. What is your preferred role in decision-making around mammography?

- I prefer to make the final decision about whether or not to get a mammogram.
- I prefer to make the final decision about whether or not to get a mammogram after seriously considering my health care provider's opinion.
- I prefer that my health care provider and I share responsibility for deciding whether or not to get a mammogram is best for me.
- I prefer that my health care provider make the final decision about whether or not I should get a mammogram, but seriously considers my opinion.
- I would prefer to leave all decisions regarding mammography to my health care provider.
- Don't know

We would like to get a sense of how much you worry about your cancer coming back. Please answer the next set of questions as honestly as possible.

29. On a scale of 1 – 6, with 6 being the most worried and 1 being the least worried, how much do you worry about your cancer coming back?

- | | | | | | |
|--------------------------|--------------------------|--------------------------|--------------------------|--------------------------|--------------------------|
|  |  |  |  |  |  |
| 1 | 2 | 3 | 4 | 5 | 6 |
| Not at all worried | | | | | very worried |

30. On a scale of 1 – 6, with 6 being the most worried and 1 being the least worried, how much do you worry about needing more tests after you have a mammogram?

-

PROTOCOL TITLE:

37. How would you define your marital status?

- Single (never married)
- Currently married or living as married
- Divorced
- Separated
- Widowed
- Don't know

38. Do you live alone or with others?

- I live alone
- I live with others

39. What is the highest level of school you have completed or the highest degree you have received?

- less than or equivalent to 8th grade
- GED or equivalent
- High school or less, no diploma
- High school graduate
- Some college or an Associate's degree
- Bachelor's degree (i.e., BA, AB, BS, BBA)
- Master's degree (i.e., MA, MS, MEngineering, MEducation, MBA)
- Professional School degree (MD, DDS, DVM, JD)
- Nursing degree
- Doctoral degree (PhD, EdD, ScD)
- Don't know
- Other

40. Do you consider yourself to be Hispanic or Latino?

- No, I am not Hispanic or Latino
- Yes, I am Hispanic or Latino
- Don't know

41. Which of the following racial groups do you most identify with?

- White or Caucasian
- Black or African American
- Asian
- American Indian or Alaska Native
- Native Hawaiian or other Pacific Islander
- Other
- Don't know

• 42. How would you describe your household's financial situation right now? (please select one answer)

- After paying the bills, you still have enough money for special things that you want.
- You have enough money to pay the bills, but little spare money to buy extra or special things.
- You have money to pay the bills, but only because you have cut back on things.

PROTOCOL TITLE:

- You are having difficulty paying the bills, no matter what you do

43. What type of health insurance do you have?

- Private health insurance plan
- Medicare A and B
- Medicare Advantage/Medicare Choice/Medicare HMO
- Medicaid
- Medicare +Federal
- Medicare +Private health insurance plan
- No Coverage
- Other

44. How confident are you filling out medical forms by yourself?

- Extremely confident
- Quite a bit confident
- Somewhat confident
- A little confident
- Not at all confident

45. How often do you have someone like a family member, friend, hospital, or clinic worker or caregiver, help you read hospital materials?

- Always
- Often
- Sometimes
- Rarely
- Never

46. How often do you have problems learning about your medical condition because of difficulty understanding written information?

- Always
- Often
- Sometimes
- Rarely
- Never

47. We would like to know how you prefer to receive health educational materials in general. Do you prefer health education materials on:

- Paper
- Computer/internet
- Web-based or mobile application
- No preference
- Other _____

48. Do you have a computer at home?

- No

PROTOCOL TITLE:

Yes

49. How would you describe your knowledge of computers?

- Excellent
- Very Good
- Good
- Fair
- Poor

50. Do you use the internet?

- No
- Yes

51. If yes, which statement below best describes how comfortable you are using the internet?

- I use the internet very comfortably
- I use the internet somewhat comfortably
- I use the internet but not comfortably
- Other _____

52. How frequently do you use the internet?

- Daily
- Once a week or less
- Less than once a week but greater than once in a month
- Once a month
- Less than once a month

53. How good are you at working with fractions?

- | | | | | | |
|--------------------------|--------------------------|--------------------------|--------------------------|--------------------------|--------------------------|
|  |  |  |  |  |  |
| Extremely
Good | Very
Good | Good | Somewhat
Good | A little bit
Good | Not at all
Good |

54. How good are you at working with percentages?

- | | | | | | |
|--------------------------|--------------------------|--------------------------|--------------------------|--------------------------|--------------------------|
|  |  |  |  |  |  |
| Extremely
Good | Very
Good | Good | Somewhat
Good | A little bit
Good | Not at all
Good |

55. How good are you at calculating a 15% tip?

- | | | | | | |
|--------------------------|--------------------------|--------------------------|--------------------------|--------------------------|--------------------------|
|  |  |  |  |  |  |
| Extremely
Good | Very
Good | Good | Somewhat
Good | A little bit
Good | Not at all
Good |

56. How good are you at figuring out how much a shirt will cost if it is 25% off?

- | | | | | | |
|--------------------------|--------------------------|--------------------------|--------------------------|--------------------------|--------------------------|
|  |  |  |  |  |  |
|--------------------------|--------------------------|--------------------------|--------------------------|--------------------------|--------------------------|

PROTOCOL TITLE:

Extremely Good Very Good Good Somewhat Good A little bit Good Not at all

57. When reading the newspaper, how helpful do you find tables and graphs that are part of a story?

Extremely Helpful Very Helpful Quite Helpful Somewhat Helpful A little Helpful Not at all Helpful

58. When people tell you the chance of something happening, do you prefer that they use words (“it rarely happens”) or numbers (“there’s a 1% chance”)?

Always prefer words Most of the time prefer words Sometimes prefer words Sometimes prefer numbers Most of the time prefer numbers Always prefer numbers

59. When you hear a weather forecast, do you prefer predictions using percentages (“there will be a 20% chance of rain today”) or predictions using only words (“there is a small chance of rain today”)?

Always prefer percentages Most of the time prefer percentages Sometimes prefer percentages Sometimes prefer words Most of the time prefer words Always prefer words

60. How often do you find numerical information to be useful?

Extremely Often Very Often Quite Often Somewhat Often A little Never

Thank you for completing the baseline questionnaire.

We will find you after your appointment to complete the second survey. If we miss you, we will call you or email you in the next 1-7 days to complete the survey by phone, email, or mail. You will receive \$40 after completing the next survey.

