If the clinician agrees, the CRC will send information and what will be used for verbal consent (Appendix F) to the patient with an opt-out number and email followed by a phone call (to those who do not opt out) to explain the study's purpose and obtain verbal consent for participation. The CRC will share a blank communication tool to the patient with the 'pre'survey to be filled out before the visit (clinic visit can be virtual or in person), and notify the clinician when a patient enrolls. This can be sent to the patient by mail or email in advance of their virtual/in person clinic visit. If the patient prefers the materials to be given to them in person, the CRC will arrange to meet the patient 30 minutes before their scheduled clinic visit. If the clinic visit is virtual, the CRC can call the patient anytime ahead of the provider visit to review the materials. The study team will be utilizing standard clinical workflows and may involve virtual substitution of office visits such as the use of Zoom Video Communications application. Although in-person office visits are preferred on site, virtual visits via Zoom conferences, which are HIPPA compliant and protected, can provide a safer and efficient alternative for patients.

Visit Day. The day before the clinic visit (virtual or in-person), the CRC will call or email the patient to remind them to fill out the 'pre'-survey and send it to the study team. We will also remind the clinician that the patient is coming/being seen virtually and will email or hand-deliver a blank communication tool before the visit so they are aware it may be discussed. The CRC may meet the patient in the waiting room or communicate by phone/email before their appointment to collect the 'pre' survey (if not already received via email/mail) A copy of the verbal consent can also be given in person or via email/mail if not already done ahead of this visit. Clinicians will be reminded to incorporate the communication tool in a way that feels comfortable to them to facilitate routine practice but without specific instructions. After the visit, the CRC

PROTOCOL TITLE:

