will ask the patient to complete the paper ‘post’ surveys in person, by mail, or by email within 7 days of the appointment, concluding the study for that patient. To understand how providers feel about the communication tool, the experience using it, and the comfort with it as a guide for discussions, the clinician will be asked to complete one brief survey per patient enrolled (no provider consent planned but a short introduction to the survey will be provided-see Appendix D), after all of their participating patients have completed their visits. Each patient will be registered to document their participation by DFCI study staff and will receive a \$40 gift card for their participation and clinicians will receive a \$40 gift card after the all surveys for participating patients have been completed. All data will be entered by the CRC into the secure, REDCap.

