- 8.4 Outcomes and Analyses for Aim 1.2. The outcomes of interest are shown in Table 2 below and have been adapted from [name] prior survey study testing a decision aid for screening mammography for older women.⁶⁶ We will focus on a primary outcome of intentions for mammography and will examine how various factors (race, health literacy, numeracy, anxiety, life expectancy) impact intentions. We use the sign rank and exact McNemar’s testing to compare the ‘pre’ vs. ‘post’ results for the continuous score for intention and proportion who indicate ‘yes’, respectively. To account for clustering by clinician, we will utilize random effects models if parametric assumptions hold, or alternatively using bootstrap resampling techniques to compute 95% confidence intervals for the change in intention. We anticipate a low number of missed surveys because of the CRC follow-up planned by phone, mail, or email if necessary. If a patient is missed for her ‘pre’ test survey, we will replace her to ensure enrollment of 45 with ‘pre’ and ‘post’ surveys. We will compare characteristics of those with missing surveys and missing questions to those with complete surveys to assess for any notable differences.

Table 2. Outcomes of Interest for Aim 1.2	
Outcome(s) of Interest	Outcome definitions, planned analyses

PROTOCOL TITLE:

Primary Outcomes: Patients: Frequency of change in intentions for mammography in the next year	15 point validated scale to assess ‘pre’ vs ‘post’ survey responses where scores 1-5 = yes to having mammography, 6-10 = unsure, 11-15 = no for mammography. We will use a continuous outcome of 1-15. ^{66,79}
Patients & Clinicians: Acceptability & Feasibility	Length, clarity; tabulate responses ⁸⁰ ; 75% report the tool is useful
Secondary Outcomes:	
Clinicians: satisfaction, time added/removed	Tabulate responses, prepare descriptive analyses
Patients: preferred decision-making role	‘Pre’ survey: Examine preferences for active, shared, passive decision-making ⁸¹
Patients: Decisional conflict	‘Pre’ vs. ‘Post’ survey: 16 item scale, Calculate total and sub-scale responses. Scores range 1-100, lower scores indicating higher quality decision-making ^{82,83}
Patients: Knowledge about mammography	Number of correct (10) knowledge questions on ‘pre’ vs. ‘post’ surveys. ^{66,84,85}

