11.0 Data Management and Confidentiality

11.1 The data analysis plan and procedures are described in Section 8.

11.2 Data Management Plan: We will use a secure, password-protected REDCap database to capture information for the intervention part of this study (Aim 1.2). Data elements to be included in the centralized study data repository will include baseline demographics, comorbidity, medications, date of diagnosis, disease characteristics, and survey information. All survey data will be specifically entered and maintained securely in password protected systems.

All study components will be run from Dana-Farber Cancer Institute. Study staff will computerize the data from the patient questionnaires in this observational study. In addition, study staff will computerize medical information on each of the study participants into the centralized, secure database. For patients invited into the study but who choose not to participate, there will be no retention of patient identifiers. Study staff will record the age, race, date of diagnosis and surgery for all patients who decline participation to allow for demographic comparison of participants and nonparticipants. All original copies of data will be kept in file cabinet locked in study staff offices. Computerized databases will be password protected. Data will be collected, coded, and managed by study staff only. The name and address file will be stored on a separate computer with password protection from the data files to protect the identity of respondents. Data and software will be backed up on a nightly basis as per our institutional norm.

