****Post-visit Patient Questionnaire****

Study ID: _____

Date: _____

Thank you for agreeing to participate in this study. Now that you have had your visit with your provider, there are a few more questions that we would like you to answer.

If your health care provider asked you right now to make a choice about whether or not to get a mammogram, on a scale from 1-15 how certain are you about whether or not you would choose to get a mammogram in the next

PROTOCOL TITLE:

year? (1 means you are sure you would get a mammogram while 15 means you are sure you would not get a mammogram, if you are unsure please give a number between 1 to 15, 8 is the middle).

1	2	3	4	5	6	7	8	9	10	11	12	13	14	15
Will Get a Mammogram					Unsure					Will Not Get Mammogram				

(**If interview is being done over the phone because the in-person visit was missed, then ask patient: From 1-15, how likely are you to get a mammogram, 1 means you are certain I will get a mammogram and 15 means you are certain you will not get a mammogram. If you are not sure, please give a number between 1 and 15 that best describes how likely you are to get a mammogram)**

2. When do you plan to get your next mammogram?

- Never
- In the next year
- More than 1 year from now but less than 2 years from now
- More than 2 years from now
- Other: _____

The next set of questions are about how you feel about whether or not to get a mammogram and are the same questions we asked you before your visit today. Please say whether you Strongly Agree, Agree, Neither, Disagree, or Strongly Disagree with the statements below.

3. I know which options are available to me for getting tested for breast cancer.

- | | | | | |
|--------------------------|--------------------------|--------------------------|--------------------------|--------------------------|
|  |  |  |  |  |
| Strongly Agree | Agree | Not sure | Disagree | Strongly Disagree |

4. I know the benefits of getting a mammogram.

- | | | | | |
|--------------------------|--------------------------|--------------------------|--------------------------|--------------------------|
|  |  |  |  |  |
| Strongly Agree | Agree | Not sure | Disagree | Strongly Disagree |

5. I know the downsides or risks of getting a mammogram.

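### The 12-month window of the primary intention item restarts at each survey (and is missing by phone), and the plan does not identify women imaged between the 'pre' survey and the visit

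*Protocol*

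**What the plan says.** Table 2 in Protocol 8.4 gives a primary outcome as "Frequency of change in intentions for mammography in the next year", on a 15-point scale where "scores 1-5 = yes to having mammography, 6-10 = unsure, 11-15 = no for mammography". Sections 8.4 and 8.5 compare 'pre' with 'post' by a signed-rank test on the score and an exact McNemar test on the proportion answering 'yes'. Aim 1.2 is a single-group pre-post study of 45 women. Section 1.0 hypothesises that fewer women will intend mammography in the next year.

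The written 'pre' item in Appendix D asks "how certain are you about whether or not you would choose to get a mammogram in the next year". The 'post' item opens "If your health care provider asked you right now to make a choice about whether or not to get a mammogram" and uses the same one-year phrase. Both forms carry a telephone alternative with no time window: "From 1-15, how likely are you to get a mammogram, 1 means you are certain I will get a mammogram".

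On timing, Section 5.3 says of the tool and 'pre' survey: "This can be sent to the patient by mail or email in advance of their virtual/in person clinic visit". It states no maximum lead time. The 'post' survey is completed "in person, by mail, or by email within 7 days of the appointment".

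The data elements named in Section 11.2 are "baseline demographics, comorbidity, medications, date of diagnosis, disease characteristics, and survey information"; no mammogram date is among them. The chart abstraction in Table 2 records whether a mammogram is scheduled, and serves a secondary outcome. 'Post' item 2 asks when the next mammogram is planned, not whether one has been done since 'pre'.

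**The concern.** The two answers being compared do not refer to the same 12 months. Take a woman with a yearly mammogram booked between 'pre' and the visit, or on the visit day before she sees the clinician. Beforehand she is sure to have one in the coming year and answers in the 1-5 range. Once it is done, her next falls at the edge of the new window or just past it, and she may answer 6 or higher. Her intention to continue is unchanged, yet she leaves the 'yes' group. A move to 'unsure' is enough for the McNemar comparison.

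For such women the shift runs in the hypothesised direction. There is no control group to show how often it occurs without the tool. Because no date is listed for collection, the sponsor might be unable to show afterwards that the effect was small. The missing window in the telephone item adds a second inconsistency: a woman who answers one survey in writing and the other by phone is asked two different questions.

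**Working it through.** **Inputs from the documents.** N = 45 with both surveys (Protocol 8.5). 'Yes' is a score of 1-5 (Table 2). Nearly 80% of survivors aged 65 or older reported a mammogram in the last year (Protocol 2.6). 'Post' is answered 0 to 7 days after the visit (5.3).

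**Not in the documents, so assumed.** Two-sided alpha of 0.05; the 'pre'-to-'post' gap w in weeks; the share of women imaged in that gap; and the share of those who then leave 'yes'. The 45 comes with no alpha, power, effect size or SD, so there is no sample-size figure to reproduce.

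**Step 1: how many switches would matter.** If k women move from 'yes' to not-'yes' and none move back, the exact two-sided McNemar p-value is 2 × 0.5^k.
- k = 5 (11% of 45): 2 × 0.03125 = 0.063
- k = 6 (13% of 45): 2 × 0.015625 = 0.031

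The exact signed-rank test with unchanged scores dropped also gives 0.031 for six changes in the same direction. With one woman moving the other way, eight are needed (p = 0.039).

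**Step 2: randomly timed imaging.** Expected number imaged in the gap = 45 × 0.8 × w/52. If half of them leave 'yes', the switching probability is q = 0.8 × (w/52) × 0.5, and the chance of at least six switches is the Binomial(45, q) upper tail.

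| Gap w | Imaged in gap | Switches if half leave 'yes' | P(at least 6 switches) |
|---|---|---|---|
| 2 weeks | 1.4 | 0.7 | 0.0001 |
| 4 weeks | 2.8 | 1.4 | 0.002 |
| 6 weeks | 4.2 | 2.1 | 0.017 |

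These are exits from 'yes' only. The sliding window also brings women in: a mammogram due 54 weeks after 'pre' is due 50 weeks after a 'post' survey answered four weeks later. With dates spread evenly over the year, entries and exits roughly balance, so the net effect is smaller than the table suggests.

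**Step 3: imaging clustered at the visit (illustration only).** Let q be the overall share of the 45 who are imaged before the visit discussion and then leave 'yes'.

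| q | Expected switches | P(at least 6 switches) |
|---|---|---|
| 10% | 4.5 | 0.29 |
| 12.5% (for example 25% paired, half switching) | 5.6 | 0.50 |
| 20% | 9.0 | 0.91 |

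No value of q can be read from the documents. The nearest statement is in 5.3, where the clinician confirms that mammography would typically be discussed at the visit. That concerns discussion, not imaging.

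**The case against.** The strongest case against is that the size is unsupported. No section says mammograms are done on or near visit days, and Step 2, the only scenario tied to a figure in the documents, is close to negligible. The gap may also be short: the coordinator reminds patients the day before the visit, may meet them 30 minutes beforehand, and seeks the 'post' survey soon afterwards. The 4-6 weeks in 5.3 is the schedule-scanning period, not a survey interval. All of this stands.

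A switch is not certain either. The item asks what the woman would choose if asked now, and one committed to yearly imaging may still answer 'yes'. That stands too, and is why half switching is only an assumption.

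Some collected data help. 'Post' item 2 separates never from later, and the surveys record the clinician's recommendation. The list in 11.2 is not closed, and staff will enter medical information. None of this commits the study to recording a mammogram done between 'pre' and the visit. 'Pre' items 31-36 are missing from the available text, but no 'pre' item could record a later event.

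A reader might infer that the artefact always runs one way, or that it is likely to produce a significant result by itself. The documents support neither. One-way bias needs imaging clustered before the visit discussion, and the 0.50 and 0.91 figures rest on assumed rates. A reader might also infer that the SAP would test this change. It names only descriptive analyses and t-tests on decisional conflict, so the testing consequence rests on Protocol 8.4-8.5.

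**Conclusion.** The mechanism holds on the text: a restarting window in the written item, no window in the telephone item, an open-ended lead time for 'pre', and no listed means of identifying women imaged after 'pre' and on or before the visit. Its size is unknown. With randomly timed imaging, the net effect is about zero to a few women of 45. It becomes material only if imaging is commonly paired with the visit, and then about six uncompensated switches would be enough for p < 0.05 in the McNemar test. This is a worthwhile, low-cost improvement to a pilot's primary outcome. It is not evidence that the result will be wrong.

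**What to change.** 1. Use the same time window in the written and telephone items of both surveys, preferably the 12 months counted from the study visit date.
2. Have the coordinator abstract from the chart the date of the last mammogram before 'pre' and the date of any mammogram between 'pre' and 'post'. For imaging on the visit day, note whether it came before or after the visit discussion.
3. Pre-specify a sensitivity analysis of the primary change that excludes women imaged after 'pre' and up to and including the visit day before the discussion, or classifies them separately using 'post' item 2. Do not exclude women imaged after the visit. That imaging may reflect the discussion, and dropping women who kept 'yes' would itself push the result in the hypothesised direction.

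The cost is two dates per patient, one extra analysis and a slight departure from the adapted item's wording. The surveys are still labelled draft in Protocol 9.3. The sample size does not change.
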